5.3.6 Treatment of patients with FVIII inhibitors

Patients who develop FVIII inhibitors during this trial may receive N8-GP and/or Treatment of bleeding episodes with by-passing agents, e.g. i.e. rFVIIa or APCC for treatment of bleeding episodes according to local standard care is allowed for patients who develop FVIII inhibitors within this trial. However, N8-GP dose levels used should not exceed 75 U/kg as a single dose and not exceed 200 U/kg as a maximum 24 hour dose. Treatment with FVIII concentrates other than N8-GP is not allowed. By-passing agents are not considered trial medication.

The ultimate goal of treatment in patients with high-titre inhibitors is to permanently eradicate the inhibitor by immune tolerance induction therapy (ITI), thereby making it possible for the patient to be treated routinely with FVIII replacement therapy again. The therapeutic concept is based on long-term uninterrupted high exposure to FVIII in an effort to sufficiently tolerise the immune system. In that state, the clinical responsiveness to FVIII replacement therapy is restored.

Novo Nordisk plans that Patients who develop inhibitors, within this trial, will be offered continued treatment with N8-GP, including ITI for a maximum of 24 months. ITI with N8-GP will not be initiated until Novo Nordisk has reviewed the clinical data available after completion of the N8-GP pivotal and surgery trial (pathfinderTM2 and pathfinderTM3), and of the paediatric PTP trial (pathfinderTM5) data needed for opening the paediatric PUP trial according to EMA requirements.

It is expected to use a N8-GP dosing regimen for ITI similar to local standard care/guidelines applied for ITI with marketed FVIII products. For each individual patient, ITI regimens with N8-GP would have to be reviewed by the investigator every month, and more formally reviewed every 3 months by Novo Nordisk.

If patients with (usually low titre) inhibitors respond well to treatment with N8-GP then the patient can continue the prophylaxis. These patients can still start ITI treatment within 6 months after the

Protocol Amendment
Trial ID: NN7088-3908

CONFIDENTIAL

Date: 20 March 2015 | Novo Nordisk
Version: 2.0

UTN: U1111-1148-1897 CONFIDENTIAL Status: Final Page: 14 of 41

confirmatory inhibitor test. If the inhibitor is still present (BU>/=0.6) at 6 months after the confirmatory test the patient must start ITI or withdraw from the trial.

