5.3.6.1 ITI therapy with N8-GP

Patients who develop inhibitors, within the pathfinderTM6 trial, will be offered continued ITI treatment with N8-GP for a maximum of 24 months. ITI therapy with FVIII concentrates other than N8-GP is not allowed within the trial. It may also be decided by the Investigator and/or parent/legal representative to withdraw the patients who developed developing FVIII inhibitors.

Patients will be evaluated after 12 months of ITI treatment, based on the level of inhibitors. If inhibitors are still positive after 12 months, but the decline from peak titre level is \geq 20%, ITI may be continued for a the total maximum period of 24 month in total.

If needed and decided by the Investigator, the initiation of the ITI can be delayed but it has to start within 6 months from the time of diagnosis of inhibitor. Inhibitor patients that commence ITI with N8-GP will follow an alternative treatment regimen and visit schedule (see Section 8.1.11).). For each individual patient, ITI regimen with N8-GP will need to be reviewed by the investigator every month, and formally reviewed every 3 months by Novo Nordisk.

The used N8-GP dosing regimen is at the discretion of the investigator, but a N8-GP dosing regimen similar to the local standard of care applied for ITI with marketed FVIII products is recommended. However, daily N8-GP dose levels used for ITI should not exceed 75 U/kg as a single dose and not exceed 200 U/kg as a maximum 24 hour dose.

The FVIII inhibitor level will be evaluated continuously in all patients that receive N8-GP for ITI. If the inhibitor disappears during the ITI (see Section 8.4.2.2), the patient should resume prophylaxis treatment as recommended in Section 5.3.2. Patients will be evaluated after 12 months and 24 months of ITI treatment, based on the level of inhibitors, within the predefined specifications of withdrawal, see Section 6.4. If inhibitors are still positive after 12 months, but the decline from peak titre level is $\geq 20\%$, ITI may continue for a maximum period of 24 month in total. For patients still with positive inhibitors after 12 months ITI, continued trial participation will be evaluated by the investigator and sponsor based on the level of inhibitors, within the predefined specifications of withdrawal criteria 8, see Section 6.4. However, if the inhibitor persists after 24 months of ITI, the patient will be withdrawn from the trial.

EudraCT No.: 2013-004025-88

 Protocol Amendment
 Date:

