6.4 Withdrawal criteria

The patient must be withdrawn if the following applies:

- 1. Dosed in the trial, but not fulfilling the inclusion and/or exclusion criteria
- 2. Anaphylactic reaction to the trial product, for definition see Section 11.1

Major surgery before 50 EDs, see Section 5.3.4

Significant thromboembolic event, see Section 11.1

Incapacity or unwillingness to follow trial procedures

Use of coagulations factors other than N8-GP or anti-coagulants unless in relation to ITI

ITI treatment has not been started within 6 months from the date of confirmation of positive FVIII inhibitor (BU $\geq 0.6 \frac{\text{ml}}{\text{ml}}$) unless the FVIII inhibitor has disappeared (BU<0.6) under continuous prophylactic treatment within the 6 months.

FVIII inhibitor titre decline from peak level is less than 20% after 12 months of ITI treatment FVIII inhibitor is positive (BU $\geq 0.6 \frac{\text{ml}}{\text{ml}}$) after 24 months of ITI treatment.

After completed ITI treatment (maximum 24 months), prophylaxis treatment as described in the protocol is not resumed/started

Positive inhibitor test result from visit 1 before first dosing (a positive sample does not have to be confirmed in a confirmatory test)

Participation in another clinical trial throughout the trial.

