5.3.6.1 ITI therapy with N8-GP

. . .

Criteria for successful assessing the outcome of ITI therapy with N8-GP:

Success: in line with international consensus¹³, and based on the mean N8-GP half-life observed in adults (18.5h) and children < 6 years of age (15h), successful N8-GP ITI outcome is based on the achievement of three stringent efficacy criteria

- Undetectable inhibitor titre < 0.6 BU
- Normalized FVIII in vivo recovery, defined as \geq 66% of expected incremental recovery
- N8-GP half-life ≥ 9 6 hours after a 72 h treatment-free washout period

Partial success:

- Reduction in inhibitor titre to $\leq 5 BU$
- Clinical effect of N8-GP therapy as judged by the investigator

Failure:

- Failure to attain defined success or partial success within 24 months of uninterrupted ITI with N8-GP
- Inhibitor decrease <20% after one year of ITI treatment

Other:

• Not fulfilling above criteria, e.g. early withdrawal from ITI treatment etc.

Once the inhibitor is confirmed to be negative, FVIII recovery should be measured after an injection of *recommended* 60 U/kg of N8-GP without washout period. When FVIII recovery is shown to be \geq 66% of the expected incremental recovery, based on PK data obtained in paediatric PTPs, a FVIII half-life study needs to be conducted after administration of *recommended* 60 U/kg of N8-GP after a 72 hours treatment-free washout period. This half-life study should be repeated, if necessary based on investigators discretion, until the half-life is confirmed to be \geq 6 hours. Blood samples for FVIII half-life evaluation should be taken pre-dose and 1h, 6h, 24 h, 48 h, and optional–72 h post-dose (see Section 8.4.2.2). If half-life is \leq 9 6 hours the ITI *therapy* should continue.

. . .

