Patients initiating ITI treatment will for the statistical analyses be considered like withdrawals and data collected during ITI treatment period will be summarised and reported separately. Evaluation of these data will be considered exploratory only.

If necessary, a statistical analysis plan (SAP) may be written in addition to the protocol, including a more technical and detailed elaboration of the statistical analyses. If created, the SAP will be finalised

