16.4.2.7 Outcome of ITI

Outcome of ITI, assessed by a predefined 4-point ITI outcome scale ("success", "partial success", "failure", "other"), for patient(s) who undergo ITI treatment during the trial, will be summarised.

Protocol Amendment no 4 Trial ID: NN7088-3908

UTN: U1111-1148-1897 EudraCT No.: 2013-004025-88

Date: Version: Status: Page:

 $14 June\ 2018$ Novo Nordisk 1.0 Final 1 of 5

Protocol Amendment

no 4

to Protocol, version 4 dated 01-November-2016

Trial ID: NN7088-3908

pathfinder™6

Safety and Efficacy of turoctocog alfa pegol (N8-GP) in Previously Untreated Patients with Haemophilia A

Trial phase: 3a

Applicable to Israel

Amendment originator:

, Clinical Trials Manager Department: Haemophilia, Clinical Operations NN IL

This confidential document is the property of Novo Nordisk. No unpublished information contained herein may be disclosed without prior written approval from Novo Nordisk. Access to this document must be restricted to relevant parties.

1 of 5

Table of Contents

Tal	ole of Contents		2
1	Introduction incl	luding rationale for the protocol amendment	3
		•	
Tal	ole of contents		3
Tal	ole 2–2	Flow chart explanatory descriptions	3

1 Introduction including rationale for the protocol amendment

Patients with congenital haemophilia A have a mutation in coagulation Factor 8 (F8) gene. The different types of mutations in the F8 gene are associated with different probabilities for development of inhibitors. Inhibitors are antibodies that neutralises the factor VIII activity thereby rendering treatment with replacement factor products, such as N8-GP, difficult.

Israel was excluded from F8 and HLA genotype testing however, since the incidence of FVIII inhibitors is the primary endpoint of the trial and certain mutations are related to very high inhibitor rates, the mutation composition of the trial population is pivotal for the understanding of the immunogenicity.

With the current protocol amendment Novo Nordisk is seeking permission to obtain the F8 genotype from the patients in Israel, if already available. If not available or if it needs to be retested, based on the investigators discretion, F8 and HLA genotype testing will be offered.

The results will be part of the clinical data analysis and reporting and used for trial specific purposes only. All information will be kept confidential.

In this protocol amendment:

- Any new text is written *in italics*.

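### The half-life required after ITI is at least 9 h in Section 8.4.2.2 but at least 6 h in Section 5.3.6.1; a smaller point is that partial success and failure can overlap on the ITI outcome scale

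*Combined protocol and SAP*

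**What the plan says.** **Half-life after ITI.** Amendment 2 put a threshold of at least 9 hours in two places: the success criteria in Section 5.3.6.1, and the PK assessment in Section 8.4.2.2, where a PK session is mandatory once ITI is complete. Section 8.1.11 (Amendment 2) requires that session before regular prophylaxis resumes and refers to 8.4.2.2 for its details. The introduction to Amendment 3 says the half-life criterion moves from 9 to 6 hours after a look at FVIII activity data from the paediatric trial NN7088-3885. Section 5.3.6.1 is edited to match.

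**ITI outcome.** Amendment 3 adds a four-category outcome to Section 4.2.2 and defines it in 5.3.6.1. Partial success is a titre reduced to 5 BU or less, together with "Clinical effect of N8-GP therapy as judged by the investigator". Failure has two bullets: "Failure to attain defined success or partial success within 24 months of uninterrupted ITI with N8-GP", and "Inhibitor decrease <20% after one year of ITI treatment". The last category, other, takes whoever fits none of these. Section 16.4.2.7 says the outcome "for patient(s) who undergo ITI treatment during the trial, will be summarised". Of the data collected during ITI, Section 16 says "Evaluation of these data will be considered exploratory only".

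**Related rules.** Section 6.4 withdraws a child if "FVIII inhibitor titre decline from peak level is less than 20% after 12 months of ITI treatment". Section 5.3.6.1 (Amendment 2) uses the same reference point: "If inhibitors are still positive after 12 months, but the decline from peak titre level is" at least 20%, ITI may run on to 24 months in total.

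**The concern.** The half-life figure governs a treatment decision. Under 5.3.6.1 it is one of three criteria for success, and ITI carries on if it is not met. Under 8.1.11 and 8.4.2.2 the same measurement comes before return to prophylaxis. If the sections carry different numbers, an investigator with a child between them gets one answer from one section and another from the other, in a decision about continuing an intensive intravenous regimen in a young child.

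The outcome scale is a reporting matter. A four-category scale has to place each child once. Partial success is an absolute rule (a titre level), and the second failure bullet is a relative rule (a fractional fall). Rules of these two kinds can both be true of one child, and the text does not say which takes precedence. A child in the overlap could be reported either way.

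**Working it through.** **1. Half-life: the texts in date order**

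| Document | Section 5.3.6.1 | Section 8.4.2.2, session after ITI |
|---|---|---|
| Amendment 2 (20 March 2015) | at least 9 h | at least 9 h |
| Amendment 3 (1 November 2016) | changed to at least 6 h | not among the listed edits, which add HCP antibodies, change a table reference and allow extra PEG antibody samples |
| Amendment 5 (13 June 2019) | half-life not touched | not touched |
| Amendment 8 (15 June 2020) | half-life not touched | only the PEG antibody text changes |

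Amendments 4, 6 and 7 are country-specific and do not touch either figure. Take a child with an inhibitor below 0.6 BU, recovery of at least 66% of expected, and a half-life of h hours:

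- h of 9 or more: both sections are satisfied.
- h below 6: neither is satisfied.
- h from 6 to below 9: success under 5.3.6.1, so ITI stops; threshold missed under 8.4.2.2.

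The conflict is confined to the third range. It does not alter the outcome category, because the category is defined in 5.3.6.1 alone.

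**2. Outcome scale: where the two rules meet**

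Inputs: the 5 BU limit and the 20% limit from 5.3.6.1 (Amendment 3); peak titre as the reference, from 5.3.6.1 (Amendment 2) and Section 6.4; and the 12-month evaluation from 5.3.6.1 (Amendment 2). Let P be the peak titre and T the 12-month titre.

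- Partial success, titre part: T ≤ 5.
- Failure, second bullet: (P − T)/P < 0.20, that is, T > 0.8P.
- Both: 0.8P < T ≤ 5, which requires P < 5/0.8 = 6.25 BU.
- A reduction to 5 BU or less presupposes a start above 5 BU, so P > 5.

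The overlap is therefore 5 < P < 6.25 BU:

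| Peak P (BU) | 0.8P (BU) | 12-month titres meeting both | Example |
|---|---|---|---|
| 5.5 | 4.40 | above 4.40, up to 5.0 | 4.8: 0.7/5.5 = 12.7% fall |
| 6.0 | 4.80 | above 4.80, up to 5.0 | 4.9: 1.1/6.0 = 18.3% fall |
| 6.2 | 4.96 | above 4.96, up to 5.0 | 5.0: 1.2/6.2 = 19.4% fall |
| 6.25 | 5.00 | none | 5.0: 1.25/6.25 = 20.0%, not below 20% |

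The child must also show clinical effect in the investigator's judgement, if both bullets under partial success are required, as I read them. The first failure bullet causes no overlap, because it excludes success and partial success by its own wording.

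**The case against.** **On the half-life.** The 9-hour sentence comes from a change list of 2015. The amendments show excerpts, and the consolidated versions that they produced are not in the file. Amendment 2 leaves some corrections unlisted, and Amendment 5 mentions administrative changes. The sponsor's intention is also plain: 6 hours, with a reason. What stands is that the consolidated text must be checked. A reader might infer that the protocol in use at sites certainly carried both numbers; the documents do not show that. But this is not a log being compared with current text. Two sections with practical force were given the same number, and the listed changes revise one of them. Amendment 2's unlisted corrections are spelling, grammar and section references, not thresholds.

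**On the outcome scale.** Withdrawal criterion 8 makes failure the natural reading when the fall is under 20% at 12 months, and a tie-break could sit in a SAP. Both points are fair. But criterion 8 removes a child from the trial without assigning an outcome. Section 16 says only that a SAP may be written, and the documents contain no SAP text that sets an order.

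Three stronger readings are tempting and should be resisted.

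- *Rebound.* A reader might infer that a child with a high peak who dips to 5 BU or less early and rebounds by month 12 meets both rules. Titres are followed continuously, but 5.3.6.1 (Amendment 2) ties formal evaluation to months 12 and 24, so an interim value does not naturally set the outcome.
- *Low titre.* Low-titre children can enter ITI: "If the inhibitor is still present (BU>/=0.6) at 6 months after the confirmatory test the patient must start ITI or withdraw from the trial". A reader might infer that any such child with a small fall meets both rules. A child never above 5 BU hardly shows a reduction to that level.
- *Size.* A reader might put a percentage-point effect on the overlap. The documents give no count of children on ITI; such a figure would be one divided by an assumed number and would not measure this flaw.

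**Conclusion.** The concern holds, in two parts of unequal weight.

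The half-life mismatch is the one that matters in practice. On the text available, a child with a half-life of 6 to under 9 hours who meets the other two criteria is a success under 5.3.6.1 and falls short under 8.4.2.2. The intended value is clearly 6 hours. The conclusion depends on the consolidated protocol not having already corrected the sentence, which cannot be checked here.

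The overlap in the outcome scale is real but minor. It needs a peak above 5 and below 6.25 BU, a 12-month titre of 5 BU or less that is still above 80% of the peak, and investigator-judged clinical effect. It assumes that the 20% is measured from peak and that both rules are applied at the 12-month evaluation. The number of children is unknown and few if any are likely to fall there. The endpoint is summarised descriptively in data labelled exploratory, so the primary endpoint and every confidence interval in the plan are untouched.

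**What to change.** 1. In Section 8.4.2.2, change the half-life after ITI from at least 9 to at least 6 hours, after checking whether the consolidated protocol already says so. This costs one number.
2. In Section 5.3.6.1, add a sentence to this effect: after success has been checked, a fall from peak titre of less than 20% at 12 months is classed as failure before partial success is considered, in line with withdrawal criterion 8; partial success is judged at the end of ITI, at most 24 months.

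Neither change needs new samples or visits. The downside of the second is that a borderline partial success becomes a failure, so the sentence should be in place before ITI outcomes are classified.

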8.4 Laboratory assessments

. . .

Laboratory results being out of normal range must be categorised as "out of normal range, not clinically significant" or "out of normal range, clinically significant". A laboratory result evaluated as "out of normal range, clinically significant" must be recorded as an AE, or if present at V0 it should be recorded as concomitant illness. Categorisation of clinical significance for out of range results may not be required for the following laboratory parameters (parts of the underlying disorder) and the investigator is therefore not required to perform a categorisation even though these parameters are listed in the laboratory report: e.g. FVIII activity, FVIII inhibitors, binding FVIII antibodies, PEG antibodies, HCP antibodies and genotype testing including HLA.

The central laboratories provide results to the trial site in the units preferred by the trial sites while the results that are transferred to the trial database will always be in SI units.

. . .

8.4.2.2. Antibody assessments

The analysis will be performed at a laboratory selected by Novo Nordisk or at a Novo Nordisk laboratory. The procedures for analyses will follow the recommendations provided by Novo Nordisk. A description of the method will be included in the final report of this trial.

Protocol Amendment
Trial ID: NN7088-3908

CONFEDENTIAL

Date: 01 November 2016 | Novo Nordisk
Version: 1.0

Status:

Page:

Final

6 of 8

UTN: U1111-1148-1897 EudraCT No.: 2013-004025-88

Plasma samples will be collected for assessment of:

N8-GP/FVIII binding antibodies

Host Cell Protein (HCP) antibodies

PEG antibodies

FVIII inhibitor

Antibody assessment should be measured according to Table 2-1 5-1. Antibody samples taken within ± 1 week from the visit (for EOT only -1 week) and send to central lab can be used for the visit assessment if the requirements for 72 hours wash out.

• • •

HCP antibodies

A selection of the samples collected for the N8-GP/FVIII binding antibody analysis will be analysed for HCP antibodies. HCP are small pieces of protein remaining from the synthesis of recombinant FVIII in CHO cells. These proteins are removed during the purification, however very small amounts may be present in the drug product and could potentially cause an immune response. This analysis will be performed depending on the amount of sample available.

The analysis of HCP antibodies is planned to include samples taken at the following time points: pre-dose prior to first N8-GP exposure and hereafter approximately every 6 months until the visit 9, hereafter every 12 months.

If deemed necessary more samples may be analysed to fully characterise the individual patient's HCP antibody profile.

PEG antibodies

Screening for PEG antibodies is based on assays that are validated according to international recognised guidelines. Samples measured above the assay cut-point will be subject to a confirmation test.

PEG antibodies should be measured according to Table 2–1 and if required, investigator may take additional PEG-antibodies samples at other visits. Samples will be analysed for PEG binding antibodies at the end of trial or whenever considered relevant.

Protocol Amendment Trial ID: NN7088-3908 UTN: U1111-1148-1897

EudraCT No.: 2013-004025-88

CONFIDENTIA

Date: Version: Status: Page:

01 November 2016 | Novo Nordisk 1.0 Final

7 of 8

8.6.1. Assessments of bleeding episodes and treatment responses

Bleeding Episode – information to be collected

Information about bleeding episodes prior to the 2 ED (V2) should always be recorded in eCRF. In case the patient is treated outside the trial site the trial site should be informed in case of a bleeding episode and the details hereof. After 2 EDs bleeding episodes must be recorded either in the eDiary (if treated at home) or in the eCRF (if treated at the trial site), see Section 12.3.

Date and time the bleeding episode started

Date and time the bleeding episode stopped

Cause of the bleeding episode

i.e. spontaneous, traumatic or due to surgery

Anatomical location of bleeding episodes

Severity of the bleeding episode, assessed by the investigator as defined in 8.6.1

Amount, and time of each dose of N8-GP

Haemostatic response assessed by the 4-point scale defined in Table 8–1

13 **Monitoring procedures**

A monitoring visit must be performed as soon as possible after FPFV and no longer than 4 weeks after. The monitoring intervals will depend on the outcome of the remote monitoring of the eCRFs, the trial site's recruitment rate and the compliance of the trial site to the protocol and GCP. The intervals between monitoring visits must not exceed 12 weeks whilst patients are in the trial at site between V0 and V14. If all patients at site are in the period after V14, intervals between monitoring visits must not exceed 26 weeks, provided on site contact at least every 12 weeks.

For screening failures: Data for the screening visit must be entered in the eCRF within preferably 3 days after data are available and the Screening Failure Form must be completed. Source data verification is not required except for informed consent, date of visit, demographics (sex, date of Protocol Amendment
Trial ID: NN7088-3908
UTN: U1111-1148-1897

Date: 01 November 2016 | Novo Nordisk
Version: 1.0 | Status: Final

Page:

8 of 8

birth and race), violated inclusion/exclusion criteria, screening failure form reason for screening failure and for data relating to any AEs if applicable. All data entered in the eCRF will be transferred into the trial database.

. . .

16 Statistical considerations

EudraCT No.: 2013-004025-88

.

Patients initiating ITI treatment will for the statistical analyses be considered like withdrawals and data collected during ITI treatment period will be summarised and reported separately. Evaluation of these data will be considered exploratory only.

If necessary, a statistical analysis plan (SAP) may be written in addition to the protocol, including a more technical and detailed elaboration of the statistical analyses. If created, the SAP will be finalised

